## 11. ASSESSMENTS

Every effort should be made to ensure that the required tests and procedures are completed as described. However, it is anticipated that there may be circumstances outside the control of the investigator, who will take all steps necessary to ensure the safety and well-being of the subject. When a protocol-required test cannot be performed, the investigator will document the reason(s) and any corrective and preventive actions taken to ensure that study processes are adhered to as soon as possible. The study team and the sponsor will be informed of these incidents in a timely fashion.

For all blood and urine collections, an effort should be made to obtain these samples at roughly the same time of day (i.e., morning or afternoon) across all visits as well as at the time periods specified in the Schedule of Activities. In addition, visits to the site must occur within the pre-defined windows outlined in this protocol, otherwise they will be considered as protocol deviations

### 11.1. Blood Volume

There will be approximately 30 PD samples of about 2cc each and 11 PK samples of 8.5 cc each drawn at each treatment visit for a total of about 214 cc of blood per visit. These two studies will be 7 to 28 days apart. There will be a 10.5 cc sample at Screening and the Follow-up Visit for a clinical chemistry panel and hematology, with an additional 15.5 cc sample at Screening for eligibility determination. A total of about 344 cc of blood will be drawn over the total study, an amount that will not exceed 4.6cc / kg body weight for a 75 kg subject (Table 6).

**Table 6: Frequency and Volume of Blood Collections**

Sample Type	Sample Volume (mL)	Number of Sampling Times			Total Volume (mL)
		Screening	Treatment Visits 1-2	Follow-Up Visit	
Clinical Chemistry	7.5	1	-	1	15
Hematology	3	1	-	1	6
HbA1c/C-peptide	3	1	-	-	3
C-peptide	5	1	-	-	5
Serology	7.5	1	-	-	7.5
Pharmacodynamics a	2	-	c. 30/visit	-	120
Pharmacokinetics	8.5	-	c. 11/visit	-	187
Total	2-8.5	5	c. 41/visit	2	343.5

a Single plasma glucose measurements at bedside via rapid glucose analyzer.

## 11.2. Clinical Laboratory Tests

The tests outlined in Table 7 will be performed at the specified time points described in the Schedule of Activities.

**Table 7: Clinical and Safety related Laboratory Tests Performed at Site**

Hematology	Chemistry	Urine	Laboratory
WBC count	Glucose	β-hCG a	HbA1c
RBC count	Creatinine	Drug screen b	C-peptide
Hemoglobin	Na +		Glucagon levels c
Hematocrit	K +		Insulin levels d
Platelet count	Ca ++		HIVab
	Albumin		HCVab
	Alkaline Phosphatase		HBsAg
	AST/SGOT		
	ALT/SGPT		

a Female participants of childbearing potential require a negative pregnancy test at Screening and prior to dosing for each of the 2 Treatment Visits. Pregnancy testing will be repeated as the Follow-up visit for safety reasons.

b Drug screening performed at Screening will include: cocaine, THC, opiates, amphetamines, methamphetamine, and phencyclidine. Except as noted below, continuation in the study requires all tests to be negative with the exception of THC, which will be noted, but will not be considered exclusionary.

c To be performed on a subset of subjects only (see Section 13.2.1).

d To be performed for individual subjects only in the event of treatment failure.

A central laboratory will be utilized for analysis of all variables with the exception of urine tests, PK samples (glucagon and insulin) and rapid plasma glucose measurements made during treatment visits. A procedures manual will be provided to each site by the central laboratory. This manual will cover procedures for the collection, processing and shipping of blood samples, along with the Clinical Laboratory Improvement Act (CLIA) certification and normal ranges for the central laboratory.

The central laboratory will provide sites with all supplies needed for collection, processing and shipping of all blood samples, including PK samples, as well as point-of-care urine pregnancy tests.

Rapid urine drug screen kits will be provided to sites by Xeris. If a subject tests positive for other than THC, the subject will normally be excluded from further study participation. However, if a subject reports use of a concomitant medication (prescription or OTC) that provides a reasonable explanation for a positive result other than THC, the subject may be allowed to participate in the study at the investigator's discretion. If the subject is not able to provide a reasonable explanation but still refutes a positive finding, a urine sample will be sent to the central laboratory for confirmation. The result of this confirmatory test will be considered definitive. The remainder of the screening visit should still be completed in this case.

A central analytical lab will analyze the PK samples collected in this study. The procedures for preparing, storing and shipping PK samples to the analytical lab will be provided in a laboratory manual that will be provided to all sites prior to the start of the study. To the extent possible based on available storage space at the sites, PK samples will be batched so as to reduce the

overall number of shipments. The main and back-up PK samples (i.e., Aliquots 1 and 2) for a particular subject should NEVER be included in the same shipment.

During treatment visits, plasma glucose levels will be measured using a bedside YSI rapid glucose analyzer. At each time point specified in Section 10, the results of both the black and white leads to one decimal place will be recorded in the source documents, with the average of the two values rounded up to the nearest one decimal place accepted as the plasma glucose level for the time point as per the following examples.

Example #1: black lead = 50.1 and white lead = 49.8

Calculation:  $50.1 + 49.8 = 99.9/2 = 49.95 = 50.0$  mg/dL recorded result

Example #2: black lead = 74.4 and white lead = 74.5

Calculation:  $74.4 + 74.5 = 148.9/2 = 74.45 = 74.5$  mg/dL recorded result

The glucose analyzer will be set to auto-calibrate following the standard practice at each site. Before each subject visit, performance checks will be made as per the standard practice at each site, and sites will maintain a log of these results.

### **11.3. Electrocardiogram (12-lead ECG)**

Single, supine 12-lead ECGs will be obtained at the pre-defined time-points outlined in Schedule of Activities as follows:

- 12-lead ECGs should be performed after the subject has rested quietly for at least 10 minutes in a supine position.
- 12-lead ECGs should be obtained before assessment of BP and heart rate, and prior to blood collections.

### **11.4. Blood Pressure and Heart Rate**

The BP and heart rate will be measured at the times specified in the Schedule of Activities. Additional or changes to collection times, or collection of BP and heart rate using automated devices is permitted, as necessary, to ensure appropriate subject's safety.

BP and heart rate will be measured in the seated position with the subject's arm supported at the level of the heart, and recorded to the nearest mmHg. The dominant arm will be used throughout the study. The subject should be rested for at least 5 min. before the BP is obtained.

Measurements of both the BP and heart rate must be taken at least 2 min. apart and recorded in the CRF.

## 12. SAFETY AND ADVERSE EVENT (AE) REPORTING

### 12.1. Definition of an Adverse Event

An AE is any untoward medical occurrence in a clinical investigation subject administered a pharmaceutical product and which is not necessarily required to have a causal relationship with this treatment. An AE can therefore be any unfavorable and unintended sign, symptom, or disease temporally associated with the use of a medicinal product, whether or not considered related to the medicinal product. Examples of AEs include:

- Abnormal test findings.
- Clinically significant symptoms and signs.
- Changes in physical examination findings which are untoward and deemed clinically significant by the investigator.
- Allergy/hypersensitivity.

The criteria for determining whether an abnormal objective test finding may be reported as an AE are as follows:

- Test result is associated with accompanying symptoms,
- Test result requires additional diagnostic testing or medical/surgical intervention,
- Test result leads to a change in study dosing or discontinuation from the study, significant additional concomitant drug treatment or other treatment.
- Test result is considered to be an AE by the investigator or Sponsor.

Repeat of a test based on an abnormal result in the absence of the above conditions does not constitute an AE. Any abnormal test result determined to be an error does not require reporting as an AE.

A treatment-emergent AE (TEAE) is an AE that either commenced following initiation of study treatment or was present prior to study treatment but increased in frequency or severity following initiation of study treatment.

Standard medical terminology should be used in describing AEs. Informal descriptions should be avoided.

### 12.2. Reporting Adverse Events

All observed or volunteered AEs regardless of treatment group or suspected causal relationship to the study treatment will be reported with two exceptions. Since it is being experimentally induced in this study, hypoglycemia will not be considered an AE in this study unless the event meets one of the definitions of an SAE (see Section 12.4). Injection site reactions will not be considered an AE unless a skin reaction or pain requires medical intervention.

For all AEs, the investigator must pursue and attempt to obtain information adequate to determine the outcome of the AE and to assess whether it meets the FDA criteria for classification as an SAE, requiring immediate notification to Xeris Pharmaceuticals. For all

AEs, follow-up by the investigator is required until the event resolves or stabilizes at a level acceptable to the investigator to consider it closed. For an unresolved AEs to be considered stable, the Medical Monitor must concur with that assessment.

As part of ongoing safety reviews conducted by the Sponsor, any non-serious adverse event that is determined to be serious (according to the FDA definitions of an SAE) will be reported by the Sponsor as an SAE. To assist in the determination of case seriousness, further information may be requested from the investigator to provide clarity and understanding of the event in the context of the clinical study.

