### 5.2. Secondary Objectives

The secondary objectives of this study are:

- To compare the pharmacodynamic characteristics of G-Pen™ (glucagon injection) 1 mg (test) versus Lilly Glucagon (glucagon for injection [rDNA origin]) 1 mg (reference) in T1D patients who are in a state of insulin-induced hypoglycemia,
- To describe and compare hypoglycemia symptom relief of the two treatments,
- To describe G-Pen™ (glucagon injection) 1 mg pharmacokinetics in the major ethnicities and races in the US: non-Hispanic Whites, Hispanics, and African-Americans; and
- To compare the safety and tolerability of G-Pen™ (glucagon injection) 1 mg (test) versus Lilly Glucagon (glucagon for injection [rDNA origin]) 1 mg (reference) in T1D patients who are in a state of insulin-induced hypoglycemia.

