  - d. Every 5±2 minutes after glucagon is administered until all symptoms have abated (i.e., all symptoms have score = 1) or 45 minutes post-dosing, whichever occurs first.
9. Local tolerability will be assessed as follows:
  - a. Subjects will complete a Visual Analog (VAS) questionnaire regarding injection site discomfort ([Appendix 2](#)) at 10±5 and 30±5 minutes post-dosing, and again at 240±5 minutes post-dosing if VAS score reported at 30 minutes is > 0 mm.
  - b. Subjects will complete an Injection Site Discomfort Description and Duration Questionnaire at 10±5 minutes post-dosing. If discomfort is ongoing at 10 minutes post-dosing, the questionnaire will be updated before the subject leaves the clinic to document the final duration.
  - c. An investigator will use the modified Draize scales ([Appendix 3](#)) to assess erythema and edema formation at the injection site at 10±5 and 30±5 minutes following administration. Any injection site with a score > 0 for either erythema or edema at 30 minutes post-dosing will be re-evaluated for both at 240±5 minutes post-dosing. If any scores remain > 1 at the 240-minute evaluation, the subject may leave the clinic but will be instructed to contact study staff if the condition fails to resolve.
10. Adverse events reported by the subject or observed by an investigator will be recorded in the CRF.

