### **12.3. Reporting Period**

For all AEs, the reporting period to Xeris Pharmaceuticals begins from the subject providing informed consent, through the Follow-up Visit. All adverse events will be followed until resolution or the subject is medically stable.

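### Injection-site reactions that start after the last scheduled rating and need no medical intervention escape the tolerability comparison and, under Section 12.2, AE reporting

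*Combined protocol and SAP*

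**What the plan says.** Local tolerability is measured only at the two treatment visits (Section 10.2.1, item 9; Table 5; Appendices 2 and 3).

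- **Draize.** The site is scored at 10 and 30 minutes. After that, "Any injection site with a score > 0 for either erythema or edema at 30 minutes post-dosing will be re-evaluated for both" signs at 240 minutes; a site with both scores at 0 is not.
- **VAS.** Discomfort is marked at 10 and 30 minutes and "again at 240±5 minutes post-dosing if VAS score reported at 30 minutes is > 0 mm".
- **Duration questionnaire.** It is opened at 10 minutes. For discomfort still present then, "the questionnaire will be updated before the subject leaves the clinic to document the final duration".
- **Persistence.** If a Draize score is still above 1 at 240 minutes, "the subject may leave the clinic but will be instructed to contact study staff if the condition fails to resolve". No later rating or recording rule follows, and a score of exactly 1 triggers no instruction.

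Section 12.2 makes two exceptions to AE reporting. One is that "Injection site reactions will not be considered an AE unless a skin reaction or pain requires medical intervention". Section 12.3 sets the general AE window: "the reporting period to Xeris Pharmaceuticals begins from the subject providing informed consent, through the Follow-up Visit".

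Table 5 lists no site rating at Visit 4. Section 9.3.3 asks for a pre-dose look at the site about to be used, which at Visit 3 is on the other side from the first dose.

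**The concern.** Moving expected local reactions from AE forms to dedicated scales is reasonable while the scales are running. Here the exemption continues after they stop. For a site scoring 0, the scale stops at 30 minutes, while the subject is still in the clinic.

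Comparing the safety and tolerability of the two products is a secondary objective (Section 5.2), and Section 13.3 names local tolerability among the variables compared between treatments. The products differ at the injection site: 0.2 mL of a DMSO-based solution from an auto-injector against 1 mL of reconstituted drug (Sections 9.3.1 and 9.3.3). If their late or lasting reactions differ, the planned data would largely not show it. Section 13.5 leaves further analysis detail to a SAP, but a SAP cannot analyse ratings that were never taken.

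**Working it through.** The plan states no figure on this point that could be reproduced. The check traces possible courses of a reaction through the rules, then sizes the rated window.

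**Tracing a reaction**

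| Course of the reaction | Rated? | AE under 12.2? | What is lost |
|---|---|---|---|
| Present at 30 min, gone by 240 | Yes, at 30 and 240 | Only if intervention needed | Nothing material |
| Present at 30 min, still there at 240 | Yes, at 30 and 240; in the 13.3.6 incidence | Only if intervention needed | Time of resolution |
| Erythema or edema above 0 at 30 min, the other sign present by 240 | Yes, both signs scored at 240 | Only if intervention needed | Nothing on presence |
| Both Draize signs 0 at 30 min, visible reaction starts before 240 | No | Only if intervention needed | The reaction itself |
| Starts after the 240-minute rating | No | Only if intervention needed | The reaction itself |

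The VAS works the same way on its own trigger: 0 mm at 30 minutes means no 240-minute mark. The triggers are separate, so a subject with a positive VAS but Draize scores of 0 at 30 minutes repeats the VAS and not the Draize. The duration entry is last updated before the subject leaves, so discomfort continuing at discharge has a truncated duration. Section 13.3.6 nevertheless plans to summarise duration.

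**Later routes into the data**

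- Visit 3: AE review, and examination of the new site only.
- Visit 4: a general physical examination and an open AE question (Section 10.2.3), with no Draize, VAS or discomfort questionnaire.
- Section 12.1 gives clinically significant examination changes and allergy or hypersensitivity as examples of AEs. Section 13.3.3 records clinically significant examination changes up to the end of the trial as AEs. Neither carries an injection-site exception; Section 12.2 does. For a clinically significant site finding that needs no intervention, they give opposite instructions.
- None of these routes feeds the Draize or VAS comparison.

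**Size of the rated window**

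Inputs: last scheduled rating at 240 minutes = 4 h (Section 10.2.1); 7 to 28 days between doses (Section 9.1); follow-up 3 to 14 days after the last dosing visit (Section 10.2.3).

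- After dose 1: 7 × 24 = 168 h and 28 × 24 = 672 h. 4/168 = 2.4%; 4/672 = 0.6%.
- After dose 2: 3 × 24 = 72 h and 14 × 24 = 336 h. 4/72 = 5.6%; 4/336 = 1.2%.
- For an instrument scoring 0 at 30 minutes: 240 − 30 = 210 minutes of the post-dose stay pass without a rating on it, or 210/240 = 87.5%.

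These are shares of time, not shares of reactions.

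**The case against.** The strongest reply is that the plan made a sensible choice. Expected local reactions go to purpose-built scales, anything needing treatment remains an AE, and the rule applies equally to both products. Each product is given once per subject, erythema and edema are only described, and the primary endpoint is untouched. This stands as a limit on how much the point matters. It does not answer the gap, because the exemption outlasts the scales.

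Three stronger readings are tempting, and the documents do not support them.

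- A reader might infer that late or persistent reactions are neither rated nor reportable. Persistent ones seen at 30 minutes are scored again at 240 and enter the incidence. Reactions needing intervention are AEs through the Follow-up Visit, and Sections 12.1 and 13.3.3 offer a further route.
- A reader might infer that the reported incidence of later reactions must be zero for both products. The same routes rule that out.
- A reader might want a count of subjects missed, or assume that rating ends at 30 minutes for most. The documents give neither a rate of late reactions nor the share scoring 0 at 30 minutes. The earlier healthy-volunteer comparison is summarised only in the Investigator's Brochure, which was not available for this review.

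A fair practical objection is that inspection days later will miss a reaction lasting hours or a day. That is true, and it is why the unconditional 240-minute rating and the change to 12.2 come first in the fix. It is also fair that making every faint score still present at discharge an AE would duplicate data already on the scale; the fix avoids this.

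**Conclusion.** The concern holds in a limited form. Reactions that first appear after the last scheduled rating and need no medical intervention are outside the tolerability comparison. They are also outside AE reporting, unless the investigator follows Section 12.1 or 13.3.3 in preference to 12.2. For reactions seen at 30 minutes and still present at 240, occurrence is captured and resolution is not.

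The gap opens at 240 minutes, or at 30 minutes on an instrument scoring 0 (for Draize, both signs 0). The rated window is at most 0.6% to 5.6% of the time to the next visit, across both doses. How many reactions fall outside it is unknown. The conclusion assumes that sites follow the schedule and Section 12.2 as written; extra, unscheduled ratings would narrow the gap. The primary non-inferiority analysis is not affected.

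**What to change.** 1. **Section 10.2.1 item 9, Appendices 2 and 3:** make the 240-minute Draize and VAS ratings unconditional at both treatment visits. Subjects are still in the clinic, and this closes the gap between 30 and 240 minutes.
2. **Section 12.2:** limit the exemption to reactions captured on the scales. Record a reaction that starts after the last rating as an AE with onset and resolution dates. For one already scored and still present at 240 minutes, record the resolution date without opening a duplicate AE.
3. **Sections 10.2.2 and 10.2.3, Table 5:** inspect and Draize-score the earlier injection site or sites before dosing at Visit 3 and during the Visit 4 physical examination. Section 9.3.3 places the two doses on different sides, so a finding can be attributed to its product.
4. **Reconcile Section 12.2 with 12.1 and 13.3.3,** so that a clinically significant site finding has one reporting rule.

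The cost is a few more ratings at visits that already take place, some text changes, and a possible slight rise in AE counts. Inspection delays would differ between first and second doses (7 to 28 days against 3 to 14 days), but the 1:1 crossover balances this across products.

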### **12.3. Reporting Period**

For all AEs, the reporting period to Xeris Pharmaceuticals begins from the subject providing informed consent, through the Follow-up Visit. All adverse events will be followed until resolution or the subject is medically stable.

### **12.4. Serious Adverse Events**

An SAE is any untoward medical occurrence at any dose which:

- Results in death
- Is life-threatening
- Requires inpatient hospitalization or extends hospitalization
- Results in persistent or significant disability
- Is another important medical event

Medical and scientific judgment is exercised in determining whether an event is an important medical event. An important medical event may not be immediately life-threatening and/or result in hospitalization or death. However, if it is determined that the event may jeopardize the subject or may require intervention to prevent a SAE outcome, the important medical event should be reported as serious. Examples of such events are intensive treatment in an emergency room or at home for allergic bronchospasm or blood dyscrasias or convulsions which do not result in hospitalization.

### **12.5. Severity Assessment**

On the AE case report forms (CRF), the investigator will use the adjectives “mild,” “moderate,” or “severe” to describe the maximum intensity of the AE. These intensity grades are defined as follows in [Table 8](#) below.

**Table 8: AE Severity Assessment**

Mild	Does not interfere with subject's usual function
Moderate	Interferes to some extent (<50%) with subject's usual function
Severe	Interferes significantly (≥50%) with subject's usual function

The terms “serious” and “severe” are not synonymous. The term “severe” is often used to describe the intensity (severity) of a specific event. The event itself, however, may be of relatively minor medical significance. This is not the same as “serious,” which is based on subject/event outcome or action criteria. Accordingly, a severe event is not necessarily a serious event.

## 12.6. Causality Assessment

The investigator will use the following question when assessing causality of an adverse event to study drug, where an affirmative answer designates the event as a suspected adverse reaction: “Is there a reasonable possibility that the drug caused the event?” A “reasonable possibility” means that there is evidence to suggest a causal relationship between the drug and the adverse event. The investigator’s assessment of causality must be provided for all AEs. The investigator must record the causal relationship in the CRF, as appropriate, and report such an assessment in accordance with the serious adverse event reporting requirements, if applicable.

